Study participants will receive \$40 per monthly study visit, with the exception of the following 3 study visits: 1) Baseline/Randomization visit, 2) Month 12 visit, and 3) Month 24 Study exit visit, for which participants will receive \$100. The modest compensation will be provided to compensate for participant's time, transportation expense, and completion of study-required procedures. Compensation will be in the form of cash or gift card and paid in installment during each monthly visit. Participants will not be required to provide receipts for reimbursement. A total of \$540 per calendar year is compensated to each subject who completes all study-related visits.

STATISTICAL ANALYSIS PLAN

Our primary study hypothesis is that *daily* oral vitamin D₃ (cholecalciferol), 3,333 IU/d (0.083 mg/d), will reduce the annual rate of respiratory events (infections, exacerbations of asthma, and the acute chest syndrome) by 50% or more during Treatment Year 1 compared with *monthly* bolus oral vitamin D₃, 100,000 IU/mo (25 mg/d) as a control. As detailed above, control treatment with bolus administration of 100,000 IU (2.5 mg/d) oral vitamin D₃ monthly should provide an estimate of the annual rates of respiratory events that would be expected with placebo treatment.

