Our primary study analysis will examine the annual rate of respiratory events (the sum of respiratory infections, asthma exacerbations and episodes of acute chest syndrome) in children with sickle cell disease randomized in a double-blind manner to the daily and monthly doses of oral vitamin D₃. The primary statistical analysis will be by "intention to treat" and will use a semiparametric regression method to estimate the between group difference in intensity (events per subject per unit of time at risk) with the assumption that covariates have a multiplicative effect on the mean and rate functions. This approach takes account of the skewed distribution of the respiratory events. The results of this analysis will be summarized as a regression parameter estimate, with the standard error of the estimate, a chi-square test with associated p-value, and a hazard ratio with confidence limits expressing the rate difference of the daily relative to the monthly group (as described in Lin, DY, Wei, LJ, Yang, I, and Ying, Z. "Semiparametric regression for the mean and rate functions of recurrent events," *J R Stat Soc Series B Stat Methodol*, 2000; 62:711–730).⁶³ This approach can adjust for group differences in time-independent covariates and estimate rate ratios at specific values of covariates and at specific times of follow up. The annualized rate of events and the average inter-event interval (in two-week intervals, the observation protocol) will be entered as time-independent covariates. After testing the initial hypothesis of overall group difference, we will sequentially test the between-treatment group differences in the study design enrollment criteria strata: age, gender and therapy (hydroxyurea). Secondary analyses using the same statistical framework will separately test the study hypotheses at the one-year time point. The functional form of covariates and proportional hazards assumptions will be checked for all models and cumulative hazard plots and cumulative residual plots will be used to display group differences in the evolution of events and model fit, respectively.

Subsidiary analyses will be made to examine a number of secondary study hypotheses with respect to the effects of vitamin D₃ on changes in pulmonary function and airway inflammation, and on immune system, but these comparisons have not entered into the sample size calculation. Data will be summarized as means \pm standard

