deviation or as counts and proportions. Study Group differences in continuous measures at baseline will be compared using independent *t* tests and differences in dichotomous categorical measures at baseline will be compared using Fisher's exact test.

Sample size

For sample size estimation, we base our estimate of the annual rate of respiratory events on the rate observed in the earlier ViDAS-1 trial in our study population, a mean annual baseline respiratory event rate of 4.1. For our estimate of the treatment effect, we use the observed reduction in annual mean respiratory event rate in the earlier ViDAS-1 trial for *monthly* bolus oral vitamin D3, 100,000 IU/mo (2.5 mg/mo), from Treatment Year 1 to Treatment Year 2 from 4.28 ± 0.36 (SEM) to 1.49 ± 0.37 , or a decrease of about 65 percent. Using a conservative estimate of a treatment effect of 50 percent reduction in the rate of respiratory events as the minimal *clinically* significant difference to be detected, **26 subjects in each group will be sufficient to detect an effect size of this magnitude with a two-sided significance level of alpha = 0.025 and 90 percent power. Allowing for as much as a 15 percent loss of participants during the two-year study (due to clinical events, such as initiating chronic red blood cell transfusion therapy, failure of compliance or exclusion or withdrawal for any reason), then our sample size estimate is $26/0.85 = 31$ participants in each treatment group, or a total of 62 participants.** Although the secondary analyses planned have not entered into the calculation of the sample size required for the proposed study, the conservative specification for the treatment effect; 90 percent power; and a generous allowance for loss of participants, should help provide adequate power for subsidiary comparisons.

Annualized Event Rate and Inter-Event-Interval (IEI)

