All primary and secondary outcome analyses will be performed under the intent-to-treat principle. Crude estimates of group differences in the annualized event rate and average inter-event-interval during Treatment Year 1 and Treatment Year 2 will be analyzed by linear mixed models for repeated measures with fixed effects for group, time and group-by-time interaction, and an AR(1) covariance structure. Analyses of secondary outcomes for pulmonary function testing will also use this approach. Further analysis of treatment group differences will be assessed using a variation of the Cox Proportional Hazards model with a counting process input of start and stop times for each event and the robust sandwich covariance estimator of Lin.⁶³ This approach models hazard for recurrence under the assumption of proportional mean processes and generates hazard ratios with 95% confidence intervals and Wald Chi-Square statistics for testing the null hypothesis. We will evaluate the influence of the event rate, average IEI as covariates and calculate between treatment group hazard ratios. We will also evaluate the influence of randomization stratifying variables as covariates of the estimate of the between treatment group difference: sex (female vs male), age (child vs adolescent) and hydroxyurea use (use vs non-use). For participants in each treatment group who withdraw from the study prior to completion of the protocol, we will repeat the primary intent-to-treat analysis with the subset of participants who completed the two-year study in a "per protocol" analysis. Finally, treatment group differences in adverse events of least grade 2 severity will be assessed with chi-square or Fisher's Exact test. We will only present comparisons of events where three or more instances are reported over the two-year treatment period.

DATA AND SAFETY MONITORING

Adherence to protocol: Conduct of the clinical trial will be in accordance with this new protocol for the ViDAS-2 study in our Investigational New Drug application. This protocol includes the appointment of a Clinical Trial Safety Officer to review laboratory results as they become available, and the formation of a Data and Safety Monitoring

Board (DSMB) consisting of an expert in pediatric sickle cell disease, a biostatistician, and a Pediatric Endocrinologist with expertise in vitamin D metabolism. The DSMB will meet bi-annually.

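### The trial is sized at two-sided alpha 0.025 but the only interval level given for the recurrent-event model is 95%, and its sandwich Wald test has no small-sample correction with 31 per arm

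*Combined protocol and SAP*

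**What the plan says.** The Sample size section takes "a mean annual baseline respiratory event rate of 4.1", a 50% reduction and a "two-sided significance level of alpha = 0.025 and 90 percent power". From these it states 26 evaluable participants per group, raised to 31 per group (62 in all) for 15% loss. No other significance level appears in the document, and 0.025 is not explained.

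The primary-analysis paragraph of the Statistical Analysis Plan specifies a semiparametric rate model for recurrent events (reference 63). Its results are to be summarised by "a chi-square test with associated p-value, and a hazard ratio with confidence limits expressing the rate difference". Neither a test level nor an interval level is given.

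Treatment Outcome Analysis describes a Cox-type model "with a counting process input of start and stop times for each event and the robust sandwich covariance estimator of Lin", citing the same reference. It "generates hazard ratios with 95% confidence intervals and Wald Chi-Square statistics for testing the null hypothesis". No finite-sample adjustment, t reference or permutation test is mentioned.

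The event rate and average inter-event interval "will be entered as time-independent covariates", and the three stratification factors are examined afterwards.

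The timing of the primary comparison is also unsettled. The primary hypothesis is a reduction "by 50% or more during Treatment Year 1", but the analysis paragraph tests the overall difference first and adds: "Secondary analyses using the same statistical framework will separately test the study hypotheses at the one-year time point".

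**The concern.** By convention the alpha used for sizing is the level at which the test is judged. A 95% interval matches a 0.05 test, so the plan pairs its 0.025 design with an interval that can point the other way. If the result falls in that window, nothing in the plan says in advance how the trial's main claim should be worded.

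The second problem is independent of the first. The sandwich variance tends to be too small when there are few independent participants, and the Wald statistic is referred to a chi-square distribution that ignores this. With 31 per arm, a test labelled 0.025 rejects a true null somewhat more often than 2.5% of the time. More model covariates would be expected to widen the gap.

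**Working it through.** **1. The plan's own figure.** The difference is 4.1 × 0.5 = 2.05 events per year. No SD is stated. Taking the ViDAS-1 SEM of 0.36 as a raw SEM on 31 per arm gives SD = 0.36 × √31 = 2.00. Then

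n = 2·SD²·(z₁₋α/₂ + z₀.₉₀)² / 2.05².

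- Two-sided 0.025: 2 × 4.018 × (2.241 + 1.282)² / 4.2025 = 23.7, so 24 per group; a t-based calculation gives 26.
- SEMs of 0.35 to 0.37 give 23–26 (z) or 24–27 (t) at 0.025. At two-sided 0.05 the same inputs need no more than 23.
- Loss: 26/0.85 = 30.6, so 31 per group and 62 in total.

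The stated 26 is thus consistent with a real two-sided 0.025. This is support, not proof, because the SD is inferred.

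**2. The window.** A two-sided 0.025 test needs |z| > 2.241; a 95% interval excludes 1 when |z| > 1.960. For example, |z| = 2.10 gives p ≈ 0.036, which misses the design alpha although the 95% interval excludes 1. On the log scale the matching 97.5% interval is wider by 2.241/1.960 = 1.144.

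**3. Null error of the uncorrected test.** The rate model with robust sandwich variance and treatment as the only term was simulated with:

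- 31 per arm and two-week bins;
- 15% of participants leaving uniformly over two years, with their partial follow-up kept;
- control means of 4.28 then 1.49 (ViDAS-1 high-dose arm, General investigational plan) for the two-year comparison, and 4.1 for Year 1;
- gamma frailty with variance k, which is assumed because the plan gives no dispersion.

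The corrected test multiplies the variance by n/(n − q) = 62/60, where q is the number of coefficients plus one, and uses t on 60 degrees of freedom. Rejection (%) at nominal 2.5%, with 40,000 replicates (Monte Carlo SE about 0.09 points) for k up to 0.5:

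| k | Two-year, uncorrected | Two-year, corrected | Year 1, uncorrected | Year 1, corrected |
|---|---|---|---|---|
| 0.05 | 3.29 | 2.68 | 3.13 | 2.47 |
| 0.25 | 3.25 | 2.57 | 3.29 | 2.57 |
| 0.5 | 3.63 | 2.92 | 3.42 | 2.80 |

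At k = 1.24 the uncorrected test gives 3.8–4.0% and the corrected test 3.1–3.2%, across both comparisons. Repeat runs moved these figures by a few tenths of a point. The rounded ranges are therefore 3.1–3.7% uncorrected and 2.5–3.0% corrected for k up to 0.5, and about 4% and 3.1–3.5% at k = 1.24.

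The range of k comes from the ViDAS-1 SEMs, using k = (SD² − mean)/mean²:

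- mean 4.28: (4.02 − 4.28)/4.28², which is about 0;
- mean 1.49: (0.37² × 31 − 1.49)/1.49² = (4.24 − 1.49)/2.22 = 1.24.

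If all of the roughly 80 participants mentioned under Subject Justification were randomized (40 per arm), the uncorrected error would still be 3.2–3.4%.

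**4. Cost of the correction.** Interval factor: √(62/60) × 2.299/2.241 = 1.043. For a constant 50% reduction, power of the 0.025 test falls by 0.1–2.8 points (for example 94.2% to 93.0% over two years at k = 0.25).

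The Study Drug section also contemplates control falling by half or more in Year 2. With a 50% effect in Year 1 only and equal Year 2 rates, the two-year ratio is (2.14 + 1.49)/(4.28 + 1.49) = 3.63/5.77 = 0.63. Power then goes from about 67% to 64% at k = 0.25 and from about 48–49% to 45–46% at k = 0.5, a loss of roughly 2.6–3.5 points.

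**5. How often the window matters (uncorrected test).** p lies between 0.025 and 0.05 in 2.6–2.9% of trials with no effect, 0.2–7.6% with a constant 50% effect, and about 9–13% when the effect is confined to Year 1 (k = 0.25–0.5).

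**The case against.** A 95% interval may be reported descriptively beside a 0.025 test, and it appears under further analyses, not in the primary-analysis paragraph. This stands in part: the mismatch is a gap in reporting and in the decision rule, not two contradictory tests. But Treatment Outcome Analysis cites the same reference for the same model, and it is the only place where an interval level or variance estimator is named.

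A reader might infer that the real type I error is 5.9–6.5%, the simulated unadjusted figure if significance is read from the 95% interval. The plan never says that it will be, so that figure should not be attributed to it.

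A reader might also infer near-doubling of the error once covariates enter. As illustration only, runs with the three stratification factors added, full follow-up, 26–31 per arm and k of 0.25 or 1 gave 3.8–4.9% at nominal 2.5%. The plan tests the overall difference first and then examines those factors; it does not clearly make an adjusted model primary. Figures for the event-rate and interval covariates are weaker still. The only annualized rate defined for this trial is a treatment-phase one, and no pre-randomization year of event collection is described. If treatment-phase values are entered, the covariates contain the outcome, which is a different problem.

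Finally, 0.025 might be suspected to be a one-sided level mislabelled. The text says two-sided, and the sample size fits that reading better.

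It is also fair that an unadjusted excess of 0.6–1.2 points for k up to 0.5 is small for a Phase 2 trial.

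**Conclusion.** The point holds in two limited parts. First, the analysis is not tied to the design alpha: a p-value between 0.025 and 0.05 misses 0.025 while the reported 95% interval excludes 1, and no rule covers that case. This rests on the text alone. Second, the unadjusted sandwich Wald test runs modestly above its nominal level. The size of that excess rests on assumed dispersion, 31 per arm and 15% dropout with partial follow-up kept. The sample size itself is not shown to be wrong, and no specific inflation can be assigned to a covariate-adjusted primary test, because the plan does not define one. The matter should be corrected before unblinding; it does not undermine the design.

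**What to change.** 1. Reconcile the Year 1 primary hypothesis with the analysis paragraph that makes the one-year test secondary, and name one primary comparison. This is a separate and larger question, but the alpha cannot be attached to a test until it is settled.
2. State that this comparison is judged at two-sided 0.025, say why that level was chosen, and report its hazard ratio with a 97.5% interval. Other comparisons can keep 95% intervals labelled descriptive.
3. Compute both the p-value and the interval from the sandwich variance times n/(n − q), with a t reference on n − q degrees of freedom. A leave-one-out sandwich with a t reference is an acceptable alternative; it gave 2.2–2.9% at nominal 2.5% in unadjusted runs with full follow-up, 26–31 per arm and k from 0 to 1.
4. If covariates are to enter the primary model, list them and define them from pre-randomization data.

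Items 2 and 3 take two or three SAP sentences and a few lines of code, with no added participants. The price is an interval 14% wider from the confidence level and about 4% wider again from the correction (1.144 × 1.043 = 1.19 in all), plus the power loss of up to about 3.5 points. At high dispersion the correction reduces the excess but does not remove it.

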Individual participant rates of events during the treatment phase (Treatment Years 1 and 2) will be annualized by dividing the number of days of observation by 365.25. Individual participant inter-event-interval (IEI) will be the average of the number of days between the first day of observation and the day of the first event and the number of days separating the resolution of one event to the onset of the subsequent event. The treatment phase IEI will be calculated as the average of the number of days separating the resolution of one event to the onset of the subsequent event, the number of days from randomization to the first event, and the days between the last event and final day of study participation. If a participant is in the midst of an event episode on the day of randomization, the calculation of the average IEI will start with the date the event resolved.

Treatment Outcome Analysis

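### The treatment-phase inter-event interval counts the unfinished gap after the last event as complete, so its value depends on length of follow-up and the one-year arm difference comes out about a fifth to a quarter too small

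*Combined protocol and SAP*

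**What the plan says.** The SAP section Annualized Event Rate and Inter-Event-Interval (IEI) defines IEI twice. The general definition, which begins "the average of the number of days between the first day of observation and the day of the first event", stops at the last event. The treatment-phase definition begins "The treatment phase IEI will be calculated as the average of the number of days separating the resolution of one event to the onset of", where what follows is a later event. It then adds the wait between randomization and a first event, and a last piece worded "and the days between the last event and final day of study participation". All pieces have equal weight, and nothing marks the last one as censored.

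Under Treatment Outcome Analysis, group differences in "average inter-event-interval during Treatment Year 1 and Treatment Year 2 will be analyzed by linear mixed models for repeated measures" with group, time and their interaction. The section calls these estimates crude and follows them with a Cox-type counting-process model with robust variance.

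IEI is also a covariate. In the opening part of the Statistical Analysis Plan, the event rate and "the average inter-event interval (in two-week intervals, the observation protocol) will be entered as time-independent covariates". Treatment Outcome Analysis repeats the idea. Neither place says which period's IEI is meant.

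**The concern.** A gap cut off by the end of participation is a lower bound on the true gap. Averaging it as if complete has two effects.

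- **Shrinkage.** A child with N events has N + 1 pieces in the average (N if the child is ill on the last day). The pull downward is strongest in children with few events, who are mostly in the daily arm if the hypothesis is true.
- **Dependence on follow-up.** The value is capped by the days observed, so a child who leaves early cannot have a long IEI. The mixed model has no term for this, and unequal loss between arms can look like a treatment difference.

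What is at stake is the reported arm difference in IEI, above all for Treatment Year 1, which is the window of the primary hypothesis. Any model that uses treatment-phase IEI as a covariate is also affected.

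**Working it through.** **Inputs.** From Sample size: "a mean annual baseline respiratory event rate of 4.1" and a "treatment effect of 50 percent reduction in the rate of respiratory events", so r = 4.1 and 2.05 per year; 15% loss over two years. Assumed: constant event rates, illnesses of 0, 7 or 10 days, and heterogeneity between children of 0 or 0.3 (gamma variance).

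**The plan's own figure.** No number is given for IEI. The rates can be tied to the stated sample size. The ViDAS-1 standard error of 0.37 with 31 per arm gives SD = 0.37 × √31 = 2.06. Then n = 2 × (2.241 + 1.282)² × (2.06/2.05)² = 25.1, rounded up to the stated 26 per group. 26/0.85 = 30.6, rounded up to the stated 31.

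**Closed form, no sick days.** IEI = T/(N + 1), with N Poisson with mean rT. Its mean is 365.25 × (1 − e^(−rT))/r days. The true mean gaps are 365.25/4.1 = 89.1 and 365.25/2.05 = 178.2 days: difference 89.1, ratio 2.00.

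| Follow-up T | r = 4.1 | r = 2.05 | Difference | Ratio | Shortfall in difference |
|---|---|---|---|---|---|
| 3 months | 57.1 | 71.4 | 14.3 | 1.25 | 84% |
| 1 year | 87.6 | 155.2 | 67.6 | 1.77 | 24% |
| 2 years | 89.1 | 175.2 | 86.2 | 1.97 | 3% |

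**Simulation with sick days** (40,000 children per arm, no heterogeneity). With 7-day illnesses the true gaps are 89.1 − 7 = 82.1 and 178.2 − 7 = 171.2 days. The one-year IEI is 81 v 151 days, a difference of 70 instead of 89 (22% too small). With 10 days the one-year difference is 71 (20% too small). Over two years with 7 days it is 82 v 169, a difference of 87 (about 3% too small). Total event-free days divided by total events gives 82 v 171 at both lengths.

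**With heterogeneity of 0.3, 7-day illnesses.** One year: IEI 102 v 168, difference 66, ratio 1.65, against a pooled 82 v 172, ratio 2.09. Two years: IEI 114 v 209, difference 96, ratio 1.84, against a pooled 82 v 170, difference 88, ratio 2.07. The ratio is attenuated at both lengths. The two-year difference in days is larger than the pooled one.

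**Loss in one arm only, no true effect** (closed form, no sick days).
- 15% leave at three months, one-year window, r = 2.05: 0.85 × 155.2 + 0.15 × 71.4 = 142.6 v 155.2, or 8% low. With 7-day illnesses the simulation gives 138 v 151, also 8%.
- 15% leave uniformly over two years, one-year window, r = 2.05: 7.5% leave in year 1, with mean IEI 365.25 × (1 − 0.425)/2.05 = 102.4. Then 0.925 × 155.2 + 0.075 × 102.4 = 151.2, or 2.6% low.
- The same loss over a two-year window, r = 4.1: leavers average 365.25 × (1 − 0.122)/4.1 = 78.2. Then 0.85 × 89.1 + 0.15 × 78.2 = 87.5, or 1.8% low.

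**Two tempting repairs.** Deleting the last gap is worse: the one-year ratio falls to 1.50, and zero-event children (about 13% of the daily arm, 2% of control) have no value. A pooled gap-time Cox model with the last gap censored recovers about 0.50 when children share one rate. It gives about 0.52-0.57 with heterogeneity of 0.3 and about 0.56-0.58 with 0.6.

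**The case against.** The strongest reply is that IEI hardly matters here. The hypothesis, the aims and the sample size concern the event rate. The recurrent-event model uses start and stop times and treats the end of follow-up correctly, and the plan itself labels the mixed-model comparison crude. All of this stands, and it limits the point to a secondary summary and to IEI as a covariate.

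It can also be said that the treatment-phase IEI runs to the end of participation, so the last gap is cut once, near month 24, and the loss is about 3%. That is fair on the definition alone. A model with Treatment Years 1 and 2 as repeated measures, however, needs a value for each year. One-year windows are therefore the natural reading, although the plan does not state a cut at month 12.

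A reader might go further and infer any of the following, which the documents and the check do not support:
- **The bias always runs toward no effect.** With heterogeneity, the two-year difference in days is not understated against pooled event-free days per event; only the ratio is.
- **Early leavers get short intervals whatever their event rate.** The cap is real, but some dependence on rate remains: 57 v 71 days at three months.
- **Dropout will create a material false difference.** The 8% needs the whole 15% loss in one arm at three months. The plan allows for 15% in the trial as a whole over two years. At 31 per arm, simulated type I error at a nominal 5% was about 5% under uniform loss and about 8% in that extreme case.

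**Conclusion.** The point holds and is minor. The treatment-phase IEI treats a censored gap as complete, and the planned mixed model ignores it. With one-year windows, the plan's rates, illnesses of 0 to 10 days and no heterogeneity, the arm difference is 20-24% too small, about 70 days instead of 89 with 7-day illnesses. Over two complete years it is about 2-4% too small. With heterogeneity of 0.3 the ratio is attenuated at both lengths, but the two-year difference in days need not be. One-sided loss can add a false difference of about 2-3% if uniform over two years, and up to about 8% if early.

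These sizes rest on constant event rates and on illness lengths and heterogeneity that the plan does not give. A reader might infer that the trial's primary result is compromised. It is not: the recurrent-event estimate without IEI as a covariate does not use this quantity.

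**What to change.** Reword the two SAP sections.

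1. In Annualized Event Rate and Inter-Event-Interval (IEI), stop averaging the final gap as a complete interval, and replace the two definitions with one. Do not simply delete the last gap.
2. In Treatment Outcome Analysis, drop the linear mixed model for IEI. Report, for each arm and treatment year, total event-free days divided by total events, with a bootstrap interval that resamples children. Zero-event children then contribute their days without a special rule.
3. State the cut at month 12 for the yearly summaries.
4. Take between-arm inference from the total-time counting-process model with robust variance that is already planned. Do not make a pooled gap-time Cox model the main replacement, since it too is attenuated when children differ in event rate.
5. Do not enter treatment-phase IEI as a covariate in the treatment comparison.

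The cost is SAP wording only: the same data, with no added visits or participants. The new summary is close to the reciprocal of the event rate, so IEI becomes descriptive.

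### The Year 1 and Year 2 event-rate contrasts use a constant-variance, equal-weight linear mixed model; if rates fall in Year 2, its Year 1 standard error is too small

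*Combined protocol and SAP*

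**What the plan says.** The SAP uses two kinds of model for respiratory events.

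- **Primary analysis (opening of the Statistical Analysis Plan).** A "semiparametric regression method to estimate the between group difference in intensity (events per subject per unit of time at risk"). The SAP justifies it by the shape of the data: "This approach takes account of the skewed distribution of the respiratory events". The Year 1 hypothesis is assigned to it as well: "Secondary analyses using the same statistical framework will separately test the study hypotheses at the one-year time point".
- **Treatment Outcome Analysis.** The quantities here are "Crude estimates of group differences in the annualized event rate and average inter-event-interval during Treatment Year 1 and Treatment Year 2"; they "will be analyzed by linear mixed models for repeated measures with fixed effects for group, time and group-by-time interaction, and an AR(1) covariance structure". The same paragraph then adds a Cox-type model with "counting process input of start and stop times for each event and the robust sandwich covariance estimator of Lin".

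The response for the mixed model is defined under Annualized Event Rate and Inter-Event-Interval: individual rates "will be annualized by dividing the number of days of observation by 365.25". Neither section gives a weight, offset or exposure term for the mixed model.

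The Study Drug section says why the trial continues into a second year: to learn whether a Year 1 benefit of daily dosing lasts, and whether monthly dosing again lowers the rate by half or more in Year 2.

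**The concern.** An AR(1) structure, as usually fitted, has one residual variance for both years. Event counts rarely behave that way, because their variance rises with their mean. The protocol expects the mean to change: in ViDAS-1 the monthly high-dose arm fell from 4.28 to 1.49 events per year between Years 1 and 2. Pooling the variance of a high-rate year with that of a low-rate year understates uncertainty in the first and overstates it in the second.

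In addition, each child contributes one rate per year with equal weight. A rate from eight weeks of observation counts as much as one from a full year, although it is far noisier.

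At stake is the year-by-year reading of the trial. The Year 2 questions are year-specific, and this model is the only one written with a group-by-time term. A false Year 1 signal from it, or a Year 2 difference missed by it, would sit beside the recurrent-event results with no rule on which governs.

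**Working it through.** **Inputs from the documents.** Control rate 4.1 per year and a 50% reduction, so 2.05 and a difference of 2.05 (Sample size). ViDAS-1 high-dose arm, n = 31: 4.28 (SEM 0.36) in Year 1 and 1.49 (SEM 0.37) in Year 2. Loss of up to 15% over two years; 31 per group enrolled.

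**Assumptions.** Between-child dispersion k is not given, so k = 0.05, 0.25, 0.5 and 1.0 were used. The timing of loss is not given. Loss is taken as non-informative.

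**1. The plan's own figure.** SD = 0.37 × √31 = 2.06. With two-sided alpha 0.025 and 90% power, n = 2 × 2.06² × (2.241 + 1.282)² / 2.05² ≈ 25.1, so 26 per group, and 26/0.85 = 30.6, so 31. The stated size reproduces. The SAP names neither formula nor SD, so this reading is inferred. It is not in dispute.

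**2. Effect of one pooled variance, complete follow-up.** Take no group difference, Year 1 rate 4.1 and Year 2 rate 1.5 in both arms. For each year V = m + k·m², and the pooled variance is P = (V1 + V2)/2. The Year 1 SE is too small by √(V1/P) and the Year 2 SE too large by √(P/V2). Approximate Year 1 type I error is 2 × [1 − Φ(1.96/√(V1/P))].

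| k | V1 | V2 | P | Year 1 SE too small by | Year 1 type I error | Year 2 SE too large by |
|---|---|---|---|---|---|---|
| 0.05 | 4.94 | 1.61 | 3.28 | 1.23 | 11.0% | 1.43 |
| 0.25 | 8.30 | 2.06 | 5.18 | 1.27 | 12.2% | 1.58 |
| 0.5 | 12.51 | 2.63 | 7.57 | 1.29 | 12.7% | 1.70 |
| 1.0 | 20.91 | 3.75 | 12.33 | 1.30 | 13.2% | 1.81 |

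**3. Simulation** (31 per arm, 2,000 runs per setting, gamma-Poisson counts, REML AR(1) mixed model fitted). Over the four values of k and the loss patterns, Year 1 type I error at nominal 5% was 8.5-13.5% for the mixed model and 4.3-6.7% for a negative binomial model with log-exposure offset. A Poisson-offset fit with robust SE reached 7.4% in one setting (k = 1.0, all losses in Year 1). With the Year 2 rate held at 4.1, the mixed model rejected in 3.6-5.6%.

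**4. Precision lost by equal weighting.** The optimal weight of a child seen 8 weeks, relative to a full-year child at rate 4.1, is (4.1 + 4.1²k) / (4.1 × 365.25/56 + 4.1²k): 0.15 at k = 0, 0.27 at k = 0.25 and 0.48 at k = 1. The mixed model uses 1. Simulated variance of the Year 1 log rate ratio, mixed model divided by negative binomial with offset:

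| Loss pattern | Variance ratio over k = 0.05 to 1.0 |
|---|---|
| Complete follow-up | 1.00 |
| 15% spread over two years | 1.02-1.11 |
| All 15% spread over Year 1 | 1.02-1.19 |
| All 15% lost in weeks 2-8 | 1.16-1.98 |

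The robust Poisson-offset fit, standing in for the planned recurrent-event model, had 1.00-1.04 times the negative binomial variance throughout.

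**The case against.** The strongest reply is that the mixed model is labelled crude and that the tests that matter already use time at risk. That stands for the primary and one-year tests. A reader might infer that the Year 1 hypothesis rests on the mixed model; the opening of the Statistical Analysis Plan says otherwise. It does not cover Year 2: the SAP says only that its primary approach can estimate rate ratios at specific follow-up times, and writes out no Year 2 contrast.

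A reader might also infer that short follow-up inflates annualized rates, or that a few early leavers dominate an arm mean. One child with 2 events in 28 days does get 2/28 × 365.25 = 26.1 per year and moves an arm mean of 31 by (26.1 − 4.1)/31 = 0.71. But at 4.1 per year the expected count in 28 days is 0.314. The Poisson chance of two or more events is therefore about 4%, and 73% of such leavers have none. Under non-informative loss the rate is unbiased; only its variance grows.

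The ViDAS-1 SEMs cut against the variance argument. They are nearly constant while the rate falls. Read as raw, they give variances of 4.02 and 4.24, hence k of about 0 in Year 1 and (4.24 − 1.49)/1.49² = 1.24 in Year 2, and pooling would then do no harm. But a pooled-variance model would itself produce near-equal SEMs, and the documents do not say how they were computed. They neither confirm nor rule out the problem.

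**Conclusion.** The point holds as a weakness in the year-specific event-rate contrasts, not in the primary or one-year tests. The more serious part is constant variance. If rates fall in Year 2 as in ViDAS-1 and variance follows the mean, Year 1 type I error from this model is about 8.5-13.5% at nominal 5%, even with complete follow-up, and the Year 2 contrast is conservative. If rates stay level, error is near 5%. Loss of precision from equal weighting is secondary: nil with complete follow-up, a variance ratio of about 1.02-1.11 under the planned loss spread over two years, and large only if losses cluster in the first weeks. A claim that a count model is always more precise would go too far; it is at least as precise in these settings, and more so when follow-up is unequal. The sizes rest on assumed dispersion, assumed timing of loss and non-informative loss.

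**What to change.** - For the Year 1 and Year 2 event-rate contrasts, specify a log-link count model (negative binomial, or Poisson GEE) with log(days observed) as offset; group, year and group-by-year terms; and robust variance by child. Adding a group-by-year term to the planned recurrent-event model would serve equally well.
- Keep the linear mixed model for pulmonary function. For event rates, keep it as description only, without tests.
- Reword the annualization sentence. Days divided by 365.25 gives years observed; the rate is events divided by (days observed/365.25).

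The cost is SAP wording and standard software, with no new data. The results become rate ratios, so report the model-based rates for each group and year, and their difference, as well.
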